9.1.2 Evaluation of aesthetic improvement

To assess the aesthetically pleasing aspect of the Radiesse hand treatment outcomes, subjects will perform self-assessments on the GAIS shown in **Table 1**. The GAIS is a relative scale therefore the subjects will be asked to perform the rating compared to baseline pre-treatment photographs.

9.1.3 Evaluation of hand function

Hand function data will be collected at enrollment and at 5 to 8 follow-up visits in all subjects with the tests listed below.

Hand function testing performed in the study will include:

- **Range of Motion** (ROM). The rROM will be assessed using a Jamar finger goniometer (Sammons Preston Rolyan, Bolingbrook, IL). This test will passively and actively measure the angle of motion of all 5 metacarpophalangeal joints in each hand by determining the flexion and extension angles. The flexion will determine how far each finger can be flexed at the metacarpophalangeal joint towards the palm. The extension will determine how each finger can be extended at the metacarpophalangeal joint away from the palm.
- Sensation. Sensation in the dorsum of each hand will be Semmes-Weinstein monofilament touch test whereby the subject will be asked to report when a light touch is felt at different areas of the dorsum of each hand.
- **Dexterity**. Fine motor skills (dexterity) will be assessed using the Functional Dexterity Test (FDT) which assesses one's ability to use the hand for daily tasks requiring 3-jaw chuck prehensions, i.e. buttoning, tying shoelaces, screwing a nut and bolt and lacing yarn. Dexterity will be measured using a 16-hole peg board (North Coast Medical, Inc., Morgan Hill, CA).
- **Strength**. Hand strength will be assessed in 2 ways; grip and pinch strengths. The grip strength will be assessed using a standard, adjustable-handle Jamar hydraulic hand dynamometer (Sammons Preston Rolyan, Bolingbrook, IL). The pinch strength will be assessed in three different ways; tip (two-point) pinch, key (lateral) pinch and palmar (three-jaw chuck) pinch using the Jamar hydraulic pinch gauge (Sammons Preston Rolyan, Bolingbrook, IL).

For the first 10 subjects enrolled at each site, hand function testing will be performed by 2 independent evaluators. After the first 10 subjects, only one evaluator will be performing the hand function testing at the required timepoints. This data will provide an assessment of intra and inter-rater variability in hand function measures within and between sites. A minimum of 50 subjects across all sites will be evaluated by two independent hand function testers.

Training of the investigators who will be conducting the hand function tests on subjects will be provided by an instructional video of a hand surgeon and hand therapist. Sponsor trainers will be qualified by direct interaction with the hand surgeon who created and codemonstrates the testing in the instructional video. Sponsor trainers worked closely with the hand surgeon during the creation of instructional video and creation of the hand function test protocol (Appendix E). To qualify, investigator trainees will be required to complete the instructional video and demonstrate to the Sponsor trainer the required competencies in accordance with the protocol for hand function testing during the Sponsor-monitored on-site training. Selection of trainees will include targeting investigators who plan to remain on staff for at least two years. Training certificates will be issued upon completion of trainee qualification. Only staff members who have been trained and qualified will be allowed to perform hand function testing during the study. Hand function test investigators will not be blinded in the study to subject group, time(s) of treatment, and time since last treatment.

9.2 Visit schedule

Screening and Enrollment

Enrollment will be limited to 250 subjects for the study. The Sponsor will oversee enrollment and be in direct communication with the investigational sites to make all efforts not to exceed the enrollment target of 250 subjects, and to ensure that Groups A and B (described in Section 7) are fully enrolled. Presenting subjects may be pre-screened to the selection criteria identified in Sections 7.2 and 7.3 above. If it is determined that a presenting subject meets these selection criteria, the subject will be given an ICF to review and sign.

Upon the subject's provision of informed consent to participate in the study, the subject will be enrolled in the study and assigned a study ID number. The number will contain 3 parts – trial identification code (GF = GradeFour), site identification number, and subject enrollment order number. For example, the third subject enrolled will receive study ID number GF-1-03. The masked evaluator will assess hands on the MHGS to meet hand rating requirements for inclusion. Enrolled subjects will be assigned to Group A or B based on baseline MHGS ratings until both groups are fully enrolled. Females of childbearing age will complete a urine pregnancy test. Study information including demographics and concomitant medications will be recorded, and photographs will be taken of each hand. After photographs, subjects will complete all of the hand function tests. If the subject is one of the first 10 enrolled at a site, the hand function tests will be repeated, as administered by a different hand function testing investigator. At this time, subjects will receive a Radiesse treatment. A take-home 30day diary will be given to the subject. A physician will assess the subject's hands for AEs. Subjects will be scheduled for a phone visit to be conducted 72 hours after treatment.

Follow-Up Evaluations

72 hours after enrollment: All subjects will be scheduled for a phone visit 72 hours after initial treatment to assess for AEs. Subjects will be reminded to continue daily entries into their 30-day diary.

Week 2: 14 ± 3 days from enrollment, all subjects will return for a follow-up visit. Changes in concomitant medications will be recorded by the study staff. Subject self-assessment of aesthetic improvement will be performed using the GAIS.

Completed entries in the take-home 30-day diary will be reviewed for completion and collected. A physician will assess the subject's hands for AEs. Photographs of the hands will be taken in the event of a device and/or injection-related severe AE, or a serious or medically concerning AE.

Month 1: 30 ± 5 days from enrollment, all subjects will return for a follow-up visit.

concomitant medications will be recorded by the study staff.

Completed entries in the take-home 30-day diary will be reviewed for completion and collected. A physician will assess the subject's hands for AEs. Hand function testing will be performed twice if the subject is one of the first 10 enrolled at a site (e.g., GF-x-01 through GF-x-10), and once if enrolled as the 11th or after (e.g., GF-x-11 and beyond). Photographs of the hands will be taken only in the event of a serious or medically concerning AE.

Month 3: 90 ± 7 days from enrollment, all subjects will return for a follow-up visit. The subject's hands will be assessed on the MHGS by a live, masked evaluator. Changes in concomitant medications will be recorded by the study staff. Subject self-assessment of aesthetic improvement will be performed using the GAIS.

A physician will assess the subject's hands for AEs. Photographs of the hands will be taken only in the event of a serious or medically concerning AE.

Month 6: 180 ± 10 days from enrollment, all subjects will return for a follow-up visit. Changes in concomitant medications will be recorded by the study staff.

assess the subject's hands for AEs.

A physician will Hand function

Changes in

testing will be performed twice if the subject is one of the first 10 enrolled at a site (e.g., GF-x-01 through GF-x-10), and once if enrolled as the 11th or after (e.g., GF-x-11 and beyond). Photographs of the hands will be taken only in the event of a serious or medically concerning AE.

Retreatment may be performed at this visit after all study data have been collected at this visit for the subject agree. If both the treating investigator and the subject agree. Females of childbearing age will complete a urine pregnancy test before retreatment if a retreatment is to be performed during this visit. If performed, the subject will receive another 30-day take-home diary on which to record AEs.

72 hours after Month 6 retreatment: Only subjects receiving a retreatment at the Month 6 visit will be scheduled for a phone visit 72 hours after treatment to assess for AEs. Subjects will be reminded to continue daily entries into their 30-day diary.

Month 7: 210 ± 5 days from enrollment, only subjects receiving a retreatment at Month 6 will return for a follow-up visit.

The take-home 30-day diary will be reviewed for completion and collected. A physician will assess the subject's hands for AEs. Hand function testing will be performed twice if the subject is one of the first 10 enrolled at a site (e.g., GF-x-01 through GF-x-10), and once if enrolled as the 11th or after (e.g., GF-x-11 and beyond). Photographs of the hands will be taken only in the event of a serious or medically concerning AE.

SOP/245/EN - CLINICAL STUDY PROTOCOL Page 31 of 48 Merz North America, Inc. Confidential and Proprietary Information. Do not disclose without authorization.

Month 12: 360 ± 30 days from enrollment, all subjects will return for a follow-up visit. Changes in concomitant medications will be recorded by the study staff.

A physician

will assess the subject's hands for AEs. Completed entries in the take-home 30-day diary will be reviewed for completion and collected. Hand function testing will be performed twice if the subject is one of the first 10 enrolled at a site (e.g., GF-x-01 through GF-x-10), and once if enrolled as the 11th or after (e.g., GF-x-11 and beyond). Photographs of the hands will be taken only in the event of a serious or medically concerning AE.

Retreatment may be performed at this visit after all study data have been collected at this visit from the subject agree. If both the treating investigator and the subject agree. Females of childbearing age will complete a urine pregnancy test before retreatment if a retreatment is to be performed during this visit. If performed, the subject will receive another 30-day take-home diary on which to record AEs.

72 hours after Month 12 retreatment: Only subjects receiving a retreatment at the Month 12 visit will be scheduled for a phone visit 72 hours after treatment to assess for AEs. Subjects will be reminded to continue daily entries into their 30-day diary.

Month 13: 390 ± 5 days from enrollment, only subjects receiving a retreatment at Month 12 will return for a follow-up visit.

The take-home 30-day diary will be reviewed for completion and collected. A physician will assess the subject's hands for AEs. Hand function testing will be performed twice if the subject is one of the first 10 enrolled at a site (e.g., GF-x-01 through GF-x-10), and once if enrolled as the 11th or after (e.g., GF-x-11 and beyond). Photographs of the hands will be taken only in the event of a serious or medically concerning AE.

Month 18: 540 ± 15 days from enrollment, all subjects will return for a follow-up visit. Changes in concomitant medications will be recorded by the study staff.

A physician

will assess the subject's hands for AEs. Completed entries in the take-home 30-day diary will be reviewed for completion and collected. Hand function testing will be performed twice if the subject is one of the first 10 enrolled at a site (e.g., GF-x-01 through GF-x-10), and once if enrolled as the 11th or after (e.g., GF-x-11 and beyond). Photographs of the hands will be taken only in the event of a serious or medically concerning AE.

Retreatment may be performed at this visit after all study data have been collected at this visit for the subject agree. If both the treating investigator and the subject agree. Females of childbearing age will complete a urine pregnancy test before retreatment if a retreatment is to be performed during this visit. If performed, the subject will receive another 30-day take-home diary on which to record AEs.

72 hours after Month 18 retreatment: Only subjects receiving a retreatment at the Month 18 visit will be scheduled for a phone visit 72 hours after treatment to assess for AEs. Subjects will be reminded to continue daily entries into their 30-day diary.

Month 19: 570 ± 5 days from enrollment, only subjects receiving a retreatment at Month 18 will return for a follow-up visit.

The take-home 30-day diary will be reviewed for completion and collected. A physician will assess the subject's hands for AEs.

Hand function testing will be performed twice if the subject is one of the first 10 enrolled at a site (e.g., GF-x-01 through GF-x-10), and once if enrolled as the 11th or after (e.g., GF-x-11 and beyond). Photographs of the hands will be taken only in the event of a serious or medically concerning AE.

Month 24: 720 ± 30 days from enrollment, all subjects will return for the final follow-up visit. Changes in concomitant medications will be recorded by the study staff.

A physician will assess the subject's hands for AEs. Hand function testing will be performed twice if the subject is one of the first 10 enrolled at a site (e.g., GF-x-01 through GF-x-10), and once if enrolled as the 11th or after (e.g., GF-x-11 and beyond). Photographs of the hands will be taken. Females of childbearing age will complete a urine pregnancy test. The subject's study participation will end at this visit.

Unscheduled Visits: Subjects will be instructed to call the investigational site if they experience significant hand discomfort or difficulty performing activities at any point during the 24 month period. At the discretion of the treating investigator, a subject will be requested to appear for an unscheduled study visit for follow-up and potential intervention for an AE of concern. For an unscheduled visit, the subject will be assessed for AEs, concomitant medication update will be obtained,

and photographs of the hands will be taken.

End of Study: The end of study will be defined as completion of all study visits by all enrolled subjects during the 24-month participation period. If an unforeseen device-related serious adverse event (SAE) or unanticipated serious device effect (USADE) occurs, the end of the study will be prolonged until clinical resolution of the event, or considered permanent as determined by the treating investigator.

Assessment	Screening/ Enrollment	Wk 2	Mo 1	Mo 3	Mo 6	Mo 7†	Mo 12	Mo 13†	Mo 18	Mo 19†	Mo 24
Visit Window	-14 to 0	Dav	Dav	Dav	Dav	Dav	Dav	Dav	Dav	Dav	Dav
(Day)		14	30	90	180	210	360	390	540	570	720
(2 4))		+-3	+- 5	+-7	+-	+-5	+-	+-5	+-	+-5	+-
					10		30		15		30
Inclusion/	X										
Exclusion	20277										
Informed	Х	Î					-		· · · · · · · · · · · · · · · · · · ·		
Consent											
Demographics	Х										
Concomitant	Х	X	X	X	X		X		X		X
Medications											
Merz Hand	Х			X							
Grading Scale			_								
 Masked 											
Evaluator											
Hand Function	X††		X††		X††	X††	X††	X††	X††	X††	X††
Testing											
Subject GAIS		Х		Х							
Urine	Х				X‡‡	2	X‡‡		X‡‡		X
Pregnancy					12.154		0.73				
Test							12	2			
Hand	Х	10			X*	σ	X*		X*		
Treatment											
72-hour	X				X**		X**		X**		
follow-up											
phone call											
Adverse	Х	X	X		X**	X	X**	X	X**	X	
Events –											
Subject Diary											
Adverse	Х	X	X	X	X	X	X	X	X	X	X
Events –											
Treating MD											
Hand	Х	Χ∞	Xţ	Xţ	Xţ	Xţ	Xţ	Xţ	Xţ	Xţ	X
Photographs											

Table 2. Schedule of Events.

[†] No visit if no treatment received one month prior

* Treatment decision at the discretion of the Treating MD in agreement with subject

†† To be performed by 2 hand function testers for first 10 subjects enrolled at each site, and by one hand function tester for all other subjects enrolled at each site.

‡ Only to document a serious or medically concerning adverse event

‡‡ Only if retreatment is to be received at this visit

** Only if retreatment is received at this visit

∞ Only to document a device and/or injection-related severe AE, or a serious or medically concerning AE

Page 34 of 48

Merz North America, Inc. Confidential and Proprietary Information. Do not disclose without authorization.

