1 SYNOPSIS

Study title

Radiesse® Post Approval Safety Study for the Treatment of Hands With Moderate to Very Severe Dorsal Volume Loss

Study phase

Device Post-Market

Study Product

Radiesse Injectable Implant

Indication

Hand augmentation to correct volume loss in the dorsum of the hand

Study objectives

The primary objective of this study is to evaluate the safety of Radiesse implantation for very severe volume loss in the dorsum of the hands at 6 months after treatment. The primary endpoint is a non-inferiority hypothesis test to demonstrate that the proportion of subjects with device/injection-related severe adverse events (AEs) in hands that were grade 4 at baseline as determined by the Merz Hand Grading Scale¹ (MHGS, **Figure 1**) is not significantly worse than the combined proportion of subjects with device/injection-related severe AEs in hands that were MHGS grades 2 or 3 at baseline.

A secondary objective of this study is to evaluate the effectiveness of Radiesse implantation for very severe volume loss in the dorsum of the hands. The effectiveness endpoints will be measured by assessing ≥ 1 point improvement from baseline in both hands of MHGS grade 4 subjects at 3- and 6-months after initial treatment.

Another secondary objective of this study is to evaluate the safety of multiple retreatments with Radiesse in the dorsum of the hands. The hypothesis is that multiple retreatments with Radiesse do not introduce new concerns of safety.

Hand function testing will also be performed by 2 test administrators at each site to evaluate the effect of Radiesse injection on hand function.

SOP/245/EN - CLINICAL STUDY PROTOCOL Page 6 of 48 Merz North America, Inc. Confidential and Proprietary Information. Do not disclose without authorization.

¹ Carruthers, et al., "A Validated Hand Grading Scale," Dermatol Surg 2008, 34:S179-S183.

Study population, diagnosis, and main criteria for in- and exclusion

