6.1.1 Study visits

Subjects will be required to present for 8 to 11 in-office visits and receive 1 to 4 followup phone calls during their 24-month study participation. If a subject only receives the initial treatment at enrollment, there will be a total of 8 visits and 1 follow-up phone call. For each of the 3 optional repeat treatments received, there will be an additional followup phone call (72-hours post injection) and a visit scheduled 1-month after each repeat treatment. The Visits will include a Screening/Enrollment/Baseline Visit in which the subject receives their first injections of Radiesse. After Enrollment, there will be a 72-hour follow-up phone call made to each subject to assess AEs and/or any changes in concomitant medications. Subjects will be seen at the study site for follow up visits at Months 1, 3, 6, 12, 18, and 24. If they are administered repeat injections at any of the Months 6, 12 and 18 visits, they will receive a 72-hour follow-up phone call following each injection and return for follow up visits 1 month post-injection at Months 7, 13, and/or 19 respectively.

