### 7.4. Additional Safety Analyses

The number and percentage of subjects experiencing physician reported TEAEs as well as the number of events itself will be reported for the following time periods:

- following initial treatment but occurring before retreatment,
- following month 6 retreatment but occurring before further retreatment,

- following month 12 retreatment but occurring before further retreatment,
- following month 18 retreatment but occurring before further retreatment.

The same will be done for subject-reported TEAEs.

Further, both, physician- and subject-reported TEAEs, will be analysed by maximum severity, by maximum duration and by number of treatments. Physician-reported TEAEs will additionally be analysed by maximum relationship.

In case of missing diary entries, the duration of a subject-reported TEAE will be calculated as follows:

- a. If the subject misses ONE day of diary entry, it is assumed that they had the event during that day they "forgot". The event will be counted as one TEAE then.
  - *i.* Example= Bruising reported on days 1, 2, 4, 5 and no diary entry on day 3; this would be a 5 day bruise of one TEAE
  - *ii.* Example= Swelling reported on days 2, 4, 5, 7 and no diary entry on day 3 or 6; this would be a 6 day swelling of one TEAE
- b. If the subject misses TWO OR MORE days of diary entry, it is assumed that they did NOT have the event during the 2 days they "forgot," and two unique TEAEs will be counted.
  - *i.* Example= Swelling reported on days 2, 3, 6, 7, 8 and no diary entry on days 4 and 5; this would be one TEAE of swelling lasting 2 days and one TEAE of swelling lasting 3 days (two unique subject-reported TEAEs)
  - *ii.* Example= Redness reported on days 1, 2, 3, 4, 7,8 and no diary entry on days 5 and 6; this would be one TEAE of redness lasting 4 days and one TEAE of redness lasting 2 days (two unique subject-reported TEAEs)

Differences between percentages of subjects with physician reported TEAEs in groups A and B will be presented together with exploratory 95% confidence intervals. The same will be done for subject-reported adverse events.

In addition, the number and percentage of subjects experiencing serious physician reported TEAEs as well as the number of events itself will be reported.

Kaplan-Meier time to event analyses will be performed for physician-reported adverse events.

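### Physician AE checks are scheduled less often after retreatment than after the first injection, so the by-period tables in SAP 7.4 cannot on their own support the retreatment-safety hypothesis

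*Protocol*

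**What the plan says.** The Protocol synopsis makes the safety of retreatment a secondary objective: "The hypothesis is that multiple retreatments with Radiesse do not introduce new concerns of safety".

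For the first injection, Protocol 9.2 places a physician assessment at the end of the enrollment visit: "A physician will assess the subject's hands for AEs. Subjects will be scheduled for a phone visit to be conducted 72 hours after treatment". Visits with a physician AE assessment follow at Week 2 ("14 ± 3 days from enrollment, all subjects will return for a follow-up visit"), Month 1, Month 3 ("90 ± 7 days from enrollment, all subjects will return for a follow-up visit") and Month 6.

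For a retreatment, Protocol 6.1.1 adds less: "there will be an additional followup phone call (72-hours post injection) and a visit scheduled 1-month after each repeat treatment". Of Month 7, Protocol 9.2 says "only subjects receiving a retreatment at Month 6 will return for a follow-up visit"; Months 13 and 19 work the same way. No visit falls 2 weeks or 3 months after a retreatment. SAP 7.5 itself notes that Months 9, 15 and 21 were never planned, but draws the consequence only for MHGS and GAIS. On the retreatment day, Protocol 9.2 says: "Retreatment may be performed at this visit after all study data have been collected at this visit".

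SAP 7.4 tabulates numbers and percentages of subjects with physician-reported TEAEs after the initial treatment and after each retreatment, for example "following month 6 retreatment but occurring before further retreatment". It does the same for subject-reported TEAEs and analyses both by number of treatments.

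**The concern.** A reader will set the initial-period column beside the retreatment columns, because these are the data that bear on the retreatment hypothesis. If physicians look less often after a retreatment, fewer physician-reported events may be found even when the true rate is the same. Taken alone, that favours the hypothesis. Week 2 is also the only follow-up visit at which Table 2 and Protocol 9.2 call specifically for photographs of a device/injection-related severe AE, and it occurs only after the first injection.

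Two further features make the columns hard to compare. The periods differ in length from subject to subject. Retreatment also depends on agreement between subject and investigator, so those retreated may be the ones who tolerated the first injection well.

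**Working it through.** **Reproducing the plan's visit count.** Protocol 6.1.1 gives 8 to 11 visits and 1 to 4 calls. Enrollment, Week 2 and Months 1, 3, 6, 12, 18 and 24 make 8 visits, with 1 call. Three retreatments add 3 visits (Months 7, 13, 19) and 3 calls: 8 + 3 = 11 visits and 1 + 3 = 4 calls. The count agrees.

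**Contacts in the 6 months after an injection** (Protocol 9.2 and Table 2, nominal days):

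| | First injection | Each retreatment |
|---|---|---|
| 72-hour call | 1 | 1 |
| Diary | 30 days | 30 days |
| Physician follow-up checks | 4 (Week 2, Months 1, 3, 6) | 2 (1 month, next 6-monthly visit) |
| First follow-up check | day 14 | day 30 |
| Longest gap between checks | 180 − 90 = 90 days | 360 − 210 = 540 − 390 = 720 − 570 = 150 days |

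The day-of-injection assessment is left out of these counts because its timing at retreatment visits is unclear (see the objection).

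**Whole periods as SAP 7.4 defines them.** Length in nominal days, then physician follow-up checks:

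| Retreated at | Initial period | Retreatment periods |
|---|---|---|
| never | 720 days, 7 | none |
| Month 18 | 540, 6 | 180, 2 |
| Month 12 | 360, 5 | 360, 3 |
| Months 12, 18 | 360, 5 | 180, 2; 180, 2 |
| Month 6 | 180, 4 | 540, 4 |
| Months 6, 18 | 180, 4 | 360, 3; 180, 2 |
| Months 6, 12 | 180, 4 | 180, 2; 360, 3 |
| Months 6, 12, 18 | 180, 4 | 180, 2; 180, 2; 180, 2 |

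The initial period lasts 180 to 720 days with 4 to 7 checks. A retreatment period lasts 180 to 540 days with 2 to 4. In a subject retreated only at Month 6, both periods have 4 checks, but the retreatment period is 540/180 = 3 times as long. Length therefore works against the detection effect in some subjects. In a subject never retreated, all 720 days count as initial period, which works the other way.

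**Size of the detection effect.** The documents give no figure for events that would be found only at the missing visits. As an illustration, assume a share *f* is lost and take the plan's 17% planning rate (Protocol 12.1, 6-month severe related AEs) as the true rate in both periods. The observed rate after retreatment is 17% × (1 − *f*): 15.3% for *f* = 10%, 12.8% for 25%, and 8.5% for 50%. These values of *f* are assumptions, and the sum ignores period length and selection.

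**The case against.** The strongest reply is that no comparison of initial and retreatment periods is planned. In SAP 7.4 the confidence intervals for differences concern Group A against Group B, and Protocol 12.1 says data after 6 months are descriptive. Early detection is also largely equal: the call, diary, 1-month physician visit and 1-month hand function test follow every injection. Protocol section 10 records AEs from consent to the last visit with start and stop dates, and subjects are told to call about significant discomfort. A missing visit may delay recording rather than lose the event.

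Most of this stands. It confines the point to physician-reported TEAEs and to events after day 30, and shows that no formal test is at risk. It does not make the columns comparable: these descriptive tables are still the evidence offered on the hypothesis, and nothing in SAP 7.4 warns the reader.

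A reader might also infer that no physician looks at the hands after a retreatment injection, making the count 5 against 2. The documents do not establish this. It rests on sentence order in Protocol 9.2, where the retreatment text is visibly broken and the order is not always chronological: the pregnancy test required before retreatment is mentioned after it. Table 2 marks a treating-physician AE assessment at Months 6, 12 and 18 without saying when in the visit it occurs, and Protocol 8.2.2 has observed AEs recorded at treatment. Nor can one infer that acute lidocaine effects would go unseen: Protocol 4.3 calls them unlikely at these doses, and the scheduled check is of the hands.

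**Conclusion.** The point holds as a limit on interpretation. Physician follow-up checks in the 6 months after an injection number 4 after the first and 2 after each retreatment, with longest nominal gaps of 90 and 150 days. Together with unequal period lengths and self-selection, this means the SAP 7.4 percentages by period and by number of treatments cannot by themselves support the retreatment hypothesis.

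A reader might conclude that the tables are bound to make retreatment look safer. That goes too far. Fewer checks push in that direction, but a longer retreatment period can push the other way, so the net direction in the full-period tables is not settled and the size is unknown. The primary 6-month test of Group A against Group B is unaffected: both groups follow the same schedule, and retreatment starts only at the Month 6 visit. The counts assume nominal visit days and full attendance.

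**What to change.** In SAP 7.4:

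- Add a table, for each injection, of diary-reported TEAEs and of physician-reported TEAEs with onset from that injection to its 1-month visit. Use AE start dates, which Protocol section 10 already requires. A split by the visit at which an event was first found is not assured, because visit of detection is not among the minimum AE fields.
- For retreated subjects, show their own rate after the first injection beside their rate after each retreatment.
- Keep the full-period tables alongside, and state that the Week 2 and Month 3 visits exist only after the first injection. Even in the early window, physicians see subjects twice after the first injection (Week 2, Month 1) and once after a retreatment. The diary rows are therefore the cleaner comparison.

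Reconcile Protocol 9.2 with Table 2 on whether the treating-physician AE assessment at Months 6, 12 and 18 comes before or after the retreatment injection. State in the SAP that events seen after the injection belong to the new treatment period.

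The cost is one or two extra tables and some wording, with no added visits and no change in sample size. The downside is that the matched table holds fewer events and says nothing about late ones, which is why the full-period tables should stay.
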